The Effects of Holding on Stress and Bonding in Mother-Infant Dyads During Therapeutic Hypothermia

Principal Investigator and Mentor: [name]
Co-Investigators: [name], MS4, [name], MS4

A. Introduction

Therapeutic hypothermia (TH) is a standard of care intervention that decreases death and disability in newborn term infants at risk for hypoxic brain injury. It involves placing the newborn infant on a cooling blanket for 72 hours in the Neonatal Intensive Care Unit (NICU). While TH has unmistakable neurological benefits to the newborn, prior research conducted with nurses and parents of infants treated with TH indicates that the experience is psychologically traumatic.¹⁻³ Specifically, both groups identified parents' inability to touch and hold their infants during TH as a major source of stress.

Past research demonstrates that the experience of being a patient in the NICU is associated with neonatal stress.⁴⁻⁶ Longitudinal studies show lasting effects of NICU-associated stress on infants as measured by persistent alterations in cortisol reactivity at eight months of age.⁷ It is likely that this stress profile also applies to infants who undergo TH while in the NICU. However, the association between TH and infant stress has not been studied quantitatively.

A complementary field of study has examined maternal holding as a therapeutic intervention for maternal and neonatal stress. Kangaroo, or skin-to-skin care, is widely used to facilitate mother-infant bonding and has been shown to have an analgesic effect on infants⁸ and cortisol lowering effects⁹ on mothers and infants. Likewise, oxytocin, a hormone produced by the pituitary gland and associated with maternal-infant bonding and stress reduction, has been shown to increase in mothers while they hold their infants¹⁴. It is unclear whether holding has the same effects during TH because skin-to-skin contact is not possible and morphine is often used to suppress infants' discomfort and shivering. The first specific aim of the present study is to evaluate the safety of allowing mothers to hold their infants during the TH protocol. The second specific aim is to investigate whether holding impacts mothers' and nurses' perception of stress during TH treatment.

[figure not shown]
B. Specific Aims and Significance

Specific Aim 1: Assess the safety and feasibility of a new holding protocol for stable infants undergoing therapeutic hypothermia in the NICU. We hypothesize that there will not be a significant change in temperature variation, and there will be no increase in adverse events during holding.

Specific Aim 2: Assess mothers' and nurses' qualitative experience related to the holding during hypothermia intervention using a questionnaire with a combination of closed and open-ended questions. We hypothesize that mothers and nurses will respond positively to the opportunity to hold during hypothermia.

Adverse Effects: Given the vulnerability of infants in the NICU, potential adverse effects of the holding intervention and the monitoring strategy for these adverse effects are outlined here.

1. Holding during hypothermia could result in unintentional rewarming of the infant due to the proximity of the normothermic mother. In order to prevent rewarming, a thermal barrier will be placed between the mother and infant and the infant's esophageal temperature will be monitored every two minutes during holding and the intervention stopped early if the infant rewarms more than 1°C. Retrospective review of 16 medical records of infants treated with hypothermia at Maine Medical Center with gestational ages ranging from 34 -40+ weeks document a usual range of temperatures during cooling from 33-34°C (goal is 33.5°C)¹⁰. The research team has made the determination that the intervention will be stopped early if the infant rewarms more than 1°C based on this data.

2. Holding during hypothermia could result in dislodging of central lines. Only experienced NICU nurses will move the infant from the isolette into the mother's arms with assistance from a member of the research team. Critically ill infants that are intubated are considered too great a risk for accidental extubation and are therefore excluded.

C. Materials and Methods

Study Design: This is a single center safety study of the feasibility of a novel holding protocol for infants undergoing therapeutic hypothermia.

Study Population: As this is a pilot study to investigate concept and feasibility, a convenience sample of ten infants and their mothers in the MMC NICU being treated with TH will be recruited for the study according to the following criteria:

Inclusion criteria:

- Infant with gestational age ≥ 35 weeks treated with therapeutic hypothermia
- Infant **without** seizures in the first 24 hours on EEG
- Infants who are clinically stable on bubble CPAP, nasal cannula or who have no respiratory support. This criterion MUST be confirmed by the Attending Neonatologist.
- Infants with all types of vascular access are eligible.
 - Use appropriate caution and attention to peripheral arterial lines and central lines (PICC, UAC, UVC, tunneled central catheters)
- Informed consent for research study signed by mother who is at MMC.

Exclusion criteria:

- Intubated status
- Use of inhaled nitric oxide
- Persistent pulmonary hypertension of the newborn
- Presence of seizures on EEG
- Use of vasopressors or paralytic agents
- Presence of chest tubes, wound vacuum or drains
- Neonatal abstinence syndrome

Eligibility for enrollment and consent process: [name] is the Neonatal Neurologist involved in the clinical care of all infants at MMC treated with therapeutic hypothermia. [name] will describe the research study to parents of infants who meet the inclusion criteria. [name] and/or the co-investigators will obtain signed informed consent from the mother on behalf of herself and from the mother or father on behalf of the infant.

Intervention: After obtaining consent, on the second or third day of hypothermia treatment, consented mothers will be assisted with holding their infants for a single 30-minute period. Holding will take place with the assistance of the NICU nurse according to the protocol developed for this study (see attached). The infant's vital signs will be measured before, during and after holding. Esophageal temperatures will also be measured and recorded every 2 minutes during holding to ensure that holding does not impact the infant's body temperature. If temperature deviations $+\text{-}1^{\circ}\text{C}$ occur or if the infant becomes hypoxic with oxygen saturations below 90%, the holding session will be terminated and the baby will be returned to his or her isolette. Prior observation of therapeutic hypothermia indicates that 1 degree Celsius is the average temperature deviation that occurs in typical therapeutic hypothermia sessions.¹⁰

Implementation of questionnaires:

- Parent Questionnaire:
A questionnaire using the Likert scale will be administered on paper to mothers 30-60 minutes after completion of the holding session. Results will be linked by a patient identification number to the hormonal samples. Responses to the questionnaire will be entered into a password-protected REDCap database.
- Nurse Questionnaire:
The nurse questionnaire starts with an alteration of consent and consists of a combination of closed and open-ended questions that will be provided to the nurse on paper at completion of the holding procedure. The nurse's questionnaire will be identified by the case number that is assigned to the mother-infant dyad to protect their identities. The results of the questionnaire will be entered into a password-protected REDCap database.

Data collected:

As all of the patients treated with therapeutic hypothermia in our NICU are recorded in the Maine Medical Center Neonatal Encephalopathy REDCap database (IRB NET976245-1), we will use the same data for this holding study. In addition to the data already recorded in the REDCap database, we will also record the infant's current medication doses during holding, temperature recording taken at 2 minute intervals during holding and their vital signs before, during, and after holding. These vital sign recordings include temperature, heart rate, blood pressure, oxygen saturation and respiratory rate. If the infant does not have an arterial line in place, blood pressure will be measured every 10 minutes using a blood pressure cuff so as not to agitate the infant.

D. Analytical Methods

- Safety
Frequency of adverse events (as defined above) will be compared in this experimental cohort to data from historical controls in our therapeutic hypothermia database.
- Questionnaires
Answers from questions using a Likert scale will be simplified into nominal agree/disagree categories and compared with χ^2 test or Fisher's Exact Test as applicable. Open-ended responses will be analyzed by Thompson's general inductive technique.

E. References

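### Aim 1's temperature-variation hypothesis has no summary, comparator, margin or interval in Section D, and the planned adverse-event comparison in ten infants is weak support for no increase

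*Combined protocol and SAP*

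**What the plan says.** Section B, Specific Aim 1, holds two safety hypotheses in one sentence: "We hypothesize that there will not be a significant change in temperature variation, and there will be no increase in adverse events during holding". Section C, Study Design, describes the trial in these terms: "This is a single center safety study of the feasibility of a novel holding protocol". Section C, Study Population, calls it a pilot and sets the size at "a convenience sample of ten infants and their mothers in the MMC NICU".

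Temperature data are planned. Under Intervention, esophageal temperatures are "measured and recorded every 2 minutes during holding to ensure that holding does not impact" body temperature, and "vital signs will be measured before, during and after holding". Data collected repeats both items and lists temperature among the vital signs. It gives no site or interval for the readings taken before and after the hold.

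Two background figures appear. Section B, Adverse Effects, reports from 16 records "a usual range of temperatures during cooling from 33-34°C (goal is 33.5°C"). Section C, Intervention, describes 1°C as the average deviation in typical sessions. Both sections use 1°C as a limit for stopping an individual session.

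Section D has two bullets, Safety and Questionnaires. The Safety bullet is one sentence: the frequency of adverse events, defined by reference back to the earlier text, is compared with historical controls from the hypothermia database. It names no test, interval or number of controls, and does not mention temperature.

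**The concern.** The first hypothesis of the first aim concerns a continuous, repeatedly measured quantity, and the analysis section does not say how that quantity will be summarised or what it will be compared with. The word significant in the hypothesis is given no size. Followed as written, the plan yields no estimate of change in temperature variation, and the event comparison carries the safety conclusion alone. If temperature is analysed anyway, the metric, the reference period and the meaning of significant would be chosen after ten infants' data have been seen. That comparison would also set aside the more informative data: an event proportion from ten infants is very imprecise, whereas about 15 readings per infant can support a useful within-infant estimate.

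**Working it through.** **1. Aim against analysis.** The plan states no power, precision, SD, event rate or margin, so it has no figure of its own to reproduce. The two hypotheses compare with Section D as follows.

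- *Change in temperature variation.* Data: a 30-minute hold read every 2 minutes, 30/2 = 15 readings per infant (16 if both ends are counted), plus temperature before and after. Analysis in Section D: none named.
- *Increase in adverse events.* Data: events in ten infants. Analysis: frequency against historical controls, with no test or interval named.

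The only route by which temperature reaches Section D is its reference back to the adverse effects. That list opens with rewarming, where "the intervention will be stopped early if the infant rewarms more than 1°C based on this data". The text does not say that a stopped session counts as an adverse event. Even if it does, a yes/no crossing does not measure variation: readings can become more variable without crossing the limit.

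**2. What ten infants say about events** (exact binomial).

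- 0/10: upper two-sided 95% limit = 1 − 0.025^(1/10) = 30.8%.
- 1/10: Clopper-Pearson interval 0.3% to 44.5%.
- Chance of 0/10 at a true rate of 10%: 0.9^10 = 34.9%.

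**3. Power of the historical comparison.** The documents give neither the test nor the number of controls. Assuming Fisher's exact test, two-sided 0.05, with true rates of 30% in the cohort and 10% in controls:

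| Controls (assumed) | Power |
|---|---|
| 16 | 18% |
| 50 | 30% |
| 100 | 38% |

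**4. What the temperature readings could give: mean change.** The 95% half-width for a within-infant change is t(0.975, 9) × SD/√10 = 2.262 × SD/3.162 = 0.715 SD. Multiplying by 0.973, the expected ratio of sample to true SD at n = 10, gives 0.70 SD. The SD of the change is not in the documents. At assumed values of 0.25 to 0.50°C the expected half-width is 0.17 to 0.35°C.

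**5. What they could give: variation.** Take the log ratio of during-hold SD to reference SD in each infant, 15 readings against 15, with a t interval over ten infants (simulated; all conditions assumed).

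| Condition | CI factor | Power, 1.25-fold rise | Power, 1.5-fold rise |
|---|---|---|---|
| Independent readings, same true ratio in all infants | 1.21 | 63% | 98% |
| Autocorrelation 0.8, SD 0.3 between infants on the log ratio | 1.44 | 22% | 59% |

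**6. The reference window.** Two conditions matter.

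- *Same length and interval.* With correlated readings the SD grows with window length. At autocorrelation 0.8, 15 readings give on average 1.7 times the SD of 3 consecutive ones (1.1 times if readings are independent; 3 is an assumed comparison).
- *Before the hold, not after.* With an assumed linear rise of 0.3°C during the hold and a mirrored fall afterwards (within-infant SD 0.1°C, autocorrelation 0.8), the SD ratio is 1.56 against a pre-hold window and 1.00 against a post-hold window. A post-hold reference can hide the effect that is sought.

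**The case against.** The strongest case on the other side has five parts.

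*Temperature is not wholly outside the plan.* Section B says that "potential adverse effects of the holding intervention and the monitoring strategy for these adverse effects are outlined here", and rewarming is the first item, so Section D's reference back plausibly takes it in. This stands. A reader might infer that the safety analysis ignores temperature, or is only a count of events. The text supports neither: a comparison with historical controls is planned, and rewarming may be one of the events compared.

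*Reference figures exist.* The 33-34°C range, the 1°C deviation and the database of treated infants are all in the documents. This also stands, but none is tied to the hypothesis as comparator or margin.

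*It is a declared ten-infant pilot.* Correct, and the size is acceptable for feasibility. The protocol nowhere says that safety will be concluded from a non-significant result, so that should not be inferred. What remains is that a hypothesis of no increase is stated with no interval to show how little ten infants can exclude.

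*The reference data may exist.* Temperature is recorded before and after the hold, and the attached holding protocol, not in the text reviewed, may give the site and interval. It would therefore be too strong to say that a change in variation cannot be recovered later. That depends on charting these documents do not describe.

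*Ten infants are also few for variation.* True: a 1.25-fold rise would be missed more often than not under the less favourable assumptions above. That is a reason to report an interval, not a reason to leave the readings unanalysed.

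**Conclusion.** The point holds in a limited form. Aim 1's first hypothesis has no stated summary, comparator, margin or interval, and temperature is analysed at most as a threshold event. The textual gap rests on no assumption. The weakness of the event result rests only on n = 10: zero events excludes only rates above about 31%. The Fisher powers of 18-38% rest on assumed rates, control numbers and choice of test. All temperature precision figures rest on assumed SDs and autocorrelation.

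A reader might go further and infer that the trial cannot address safety, or that ten infants are too few for its purpose. The documents do not support that. The trial is a pilot, the during-hold readings are already to be collected, and a within-infant analysis of them is feasible. This is a cheap improvement that should be made, not a flaw that defeats the design.

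**What to change.** Restate Aim 1 as estimation and add to Section D:

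> For each infant we will compute: (a) mean esophageal temperature during the hold minus the pre-hold esophageal value, summarised over infants as a mean with 95% CI against an analysis margin fixed before enrolment; (b) the within-infant SD during the hold and its ratio to the SD over a pre-hold window of the same length and 2-minute interval from the existing probe, summarised as a geometric mean ratio with 95% CI, or, if no such window is available, the during-hold SD reported descriptively; post-hold readings are summarised separately and are not used as the reference; (c) the maximum excursion in either direction from the pre-hold value, listed by infant. Early-terminated holds are included up to termination, with duration reported. (d) Adverse events are reported as k/10 with an exact 95% CI, and the historical comparison is descriptive. (e) Safety will not be concluded from non-significance or from no observed increase.

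State whether a stopped session counts as an adverse event. Before the analysis margin is set, the trial team should reconcile its own temperature passages: Section B stops for rewarming beyond 1°C while Section C, Intervention, stops for a 1°C deviation in either direction; and Section B gives a usual range of 33-34°C while Section C calls 1°C the average deviation. It should also confirm that the pre-hold temperature is esophageal.

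Cost: a few lines of text and no added infants. If pre-hold esophageal readings are not already charted every 2 minutes, item (b) needs one set of about 15 per infant from the existing probe, or falls back to the descriptive report. The downside is a less favourable safety statement, since 0/10 leaves rates up to about 31% open, and modest changes in variation will stay uncertain (power of about 22-63% for a 1.25-fold rise under the assumed conditions).

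### Aim 1's temperature hypothesis has no planned analysis of temperature as a continuous measure; at most, rewarming above about 1°C is counted yes or no

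*Combined protocol and SAP*

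**What the plan says.** Section B, Specific Aim 1, joins two hypotheses in one sentence: that "there will not be a significant change in temperature variation", and that adverse events will not become more frequent with holding. The temperature hypothesis is therefore distinct from the adverse-event hypothesis. The term for temperature variation is not defined.

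Section C, Intervention, has esophageal temperature "recorded every 2 minutes during holding to ensure that holding does not impact" body temperature. Section C, Data collected, introduces the study-specific items with "In addition to the data already recorded in the REDCap database, we will also record", and these include "temperature recording taken at 2 minute intervals during holding and their vital signs before, during, and after holding". Temperature is listed among the vital signs, so a pre-hold value will exist, although its measurement site is not given.

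Section B, Adverse Effects, item 1, names rewarming as a potential harm and cites a review of 16 local records with a usual range of 33–34°C around a 33.5°C goal. From this it sets the rule that the hold is "stopped early if the infant rewarms more than 1°C based on this data". Section C, Intervention, applies the limit in both directions and describes 1°C as the average deviation seen in ordinary cooling.

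Section D has two entries. Under Safety: "Frequency of adverse events (as defined above) will be compared in this experimental cohort to data from historical controls in our therapeutic hypothermia database". Under Questionnaires, it covers Likert and open-ended answers, and the chi-square and Fisher tests belong to that entry only.

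**The concern.** One of the two Aim 1 hypotheses has no summary measure, comparator, interval or decision criterion. The most the plan offers is an event count in which rewarming might be included.

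Such a count cannot register a shift that stays under the cut-off. If holding warmed most infants by a few tenths of a degree, the study could report no rewarming events while its own recorded data showed a systematic change. The temperature hypothesis would then go unanswered, or be answered by a method chosen after the data were seen. Rewarming is the first harm the protocol lists, so this bears on the main safety question.

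**Working it through.** The plan gives no sample-size calculation, SD or margin for temperature, so there is no stated figure to reproduce. The check is a comparison of sections, followed by arithmetic on what the available data could show.

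**1. Hypothesis against analysis**

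| Aim 1 hypothesis | Data collected (Section C) | Analysis (Section D) |
|---|---|---|
| No increase in adverse events | Events, historical database | Frequency against historical controls |
| No significant change in temperature variation | Pre-hold and post-hold values, reading every 2 minutes | None as a continuous measure; possibly a yes/no count |

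**2. Data available.** One 30-minute hold with a reading every 2 minutes gives 30 / 2 = 15 readings (16 if time zero is counted). For ten infants that is 150 to 160 readings, plus pre-hold and post-hold values.

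**3. What an event count can show.** With 0 events in n = 10, the exact upper bound is 1 − α^(1/n):

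- one-sided 95%: 1 − 0.05^(1/10) = 0.259, or 26%
- upper limit of the two-sided 95% interval: 1 − 0.025^(1/10) = 0.308, or 31%

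These bounds follow from the sample size and would apply to any yes/no outcome in ten infants. They show how little a clean count would establish.

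**4. What a paired change can show.** The 95% CI half-width for a mean within-infant change is t(0.975, 9) × SD / √10 = 2.262 × SD / 3.162 = 0.715 × SD. The documents give no SD of change, so a range is assumed:

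| Assumed SD of change | Half-width |
|---|---|
| 0.2°C | 0.14°C |
| 0.35°C | 0.25°C |
| 0.5°C | 0.36°C |

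**5. When the count misses a shift.** Suppose, for illustration only, a true mean end-of-hold rise of 0.5°C. The 1°C limit then lies (1.0 − 0.5) / SD above the mean:

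- SD 0.2°C: 2.5 SDs. Few infants would cross it. A study observing this mean and SD would have a CI of 0.5 ± 0.14, or 0.36 to 0.64°C, which is clearly above zero.
- SD 0.5°C: 1 SD. Some infants would probably cross it, so the count would be less blind.

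The count therefore fails mainly when infants respond alike. I attach no probability to this. It would rest on an assumed rise and SD, and it falls further once the stop is applied to every reading and not just the last.

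**6. Clinical scale.** A rise of 0.5°C from the 33.5°C goal gives 34.0°C, the top of the stated usual range and still inside it.

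**7. Why the maximum should not be tested against zero.** The expected maximum of 15 independent standard normal readings is 1.74. With an assumed reading noise of SD 0.1°C and no drift, the maximum exceeds the starting level by about 1.74 × 0.1 = 0.17°C on average, by chance alone.

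**The case against.** The strongest defence is that temperature is already inside the safety analysis. Rewarming is item 1 under Adverse Effects, and Section D counts adverse events by reference back to earlier text. Section C also gives 1°C as the usual deviation during cooling, so no change in variation may simply mean no deviation beyond that benchmark. This reading is plausible, and it is why the point is limited to temperature as a continuous measure. It does not close the gap. Aim 1 states the two hypotheses separately, the back-reference is loose, and a yes/no count does not describe variation.

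It is also fair that this is a ten-infant pilot of concept and feasibility, and that the readings can still be described at reporting. What is lost is prespecification, not data.

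A reader might infer three stronger things that the documents do not support:

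- **That the readings go unused or infants are unprotected.** Every reading feeds the bedside ±1°C stop.
- **That a rise below 1°C is harmful.** Nothing in the text says so.
- **That the historical controls have no usable temperatures.** The text shows only that the 2-minute readings are additional to the existing database, so it gives no sign that controls have readings at that spacing.

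The attached holding protocol is not in the supplied text. Section C cites it for how holding is carried out, and Section D does not refer to it.

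**Conclusion.** The point holds as a gap in the planned analysis and should be fixed. Followed as written, Section D brings temperature into the Aim 1 result at most as a count of rewarming above about 1°C. A clean count of 0 in 10 would still be compatible with an event rate of up to 26% (one-sided) or 31% (two-sided). A paired analysis of data largely planned already would estimate the mean change to within about 0.14 to 0.36°C.

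The missing analysis and the count bounds rest on the documents alone. The precision range rests on assumed SDs of 0.2 to 0.5°C and on all ten infants contributing. How much a count would miss depends on the spread between infants: a lot if they respond alike, less if the SD is near 0.5°C. Infant protection during the hold is unaffected.

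**What to change.** Leave the 1°C stop as it is. Add one short paragraph to Section D:

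- **Measures.** For each infant, the change from the pre-hold temperature to (a) the last reading of the hold and (b) the mean of the 2-minute readings. Specify that the pre-hold value is taken at the esophageal site, since Section C names that site only for readings during the hold.
- **Estimate and criterion.** Give a 95% CI for each mean change. Judge it against a prespecified margin no wider than the protocol's own 1°C benchmark, and not by a non-significant p-value. A margin of 0.5°C, the distance from the goal to the top of the usual range, is one candidate; the choice is clinical.
- **Variation.** List each infant's maximum change and range during the hold. Do not test the maximum against zero.
- **Early stops.** Keep these infants, with values up to the stop, and flag them.
- **Event count.** State whether rewarming counts as an adverse event, and at what cut-off.
- **Limitation.** State that a pre-post change without controls cannot separate holding from handling or ordinary drift. If charting allows, compare with 30-minute changes in cooled infants who were not held.

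The costs are a little more analysis and a CI that may be wide with ten infants (half-width about 0.72 × SD). The rise will be understated in infants stopped early, and the safety statement may be less favourable. No new data are needed if the pre-hold temperature is esophageal.

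### A dislodged central line is the only device loss named as a potential adverse effect of holding, so the safety count may be incomplete for other lines, respiratory interfaces and the esophageal probe

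*Combined protocol and SAP*

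**What the plan says.** Section B introduces its list as follows: "potential adverse effects of the holding intervention and the monitoring strategy for these adverse effects are outlined here". The list has two items. The first is thermal: "Holding during hypothermia could result in unintentional rewarming of the infant due to the proximity of the normothermic mother". The second concerns devices: "Holding during hypothermia could result in dislodging of central lines". Item 2 also mentions accidental extubation, but only as a reason for exclusion: "Critically ill infants that are intubated are considered too great a risk for accidental extubation and are therefore excluded".

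The inclusion criteria in section C admit a wider range of devices. On respiratory support: "Infants who are clinically stable on bubble CPAP, nasal cannula or who have no respiratory support". On access: "Infants with all types of vascular access are eligible", followed by the instruction "Use appropriate caution and attention to peripheral arterial lines and central lines". Temperature during holding comes from an esophageal measurement every 2 minutes. A temperature deviation of 1°C or a saturation below 90% ends the session.

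Section C, Data collected, adds medication doses, the 2-minute temperatures and vital signs to the existing database. Section D, Safety, states the endpoint: "Frequency of adverse events (as defined above) will be compared" with historical controls.

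**The concern.** Safety is Specific Aim 1, and the hypothesis is that adverse events do not increase during holding. The intervention lifts an infant with several attached devices out of the isolette, keeps the infant in the mother's arms for 30 minutes and returns the infant. Displacing a device is among the most direct mechanical harms that this can cause.

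The endpoint points back to an earlier definition, and the section B list is the only passage that reads like one. That list names one class of device. The caution about peripheral arterial lines in section C shows that the authors foresaw a handling risk beyond central lines, yet that risk is not carried into the list. If the list is applied as written, a hold in which a peripheral arterial line or a cannula came out could be reported as free of adverse events. With ten infants, one event more or less is the difference between 0/10 and 1/10.

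**Working it through.** The plan states no adverse-event rate, margin, alpha or power, and ten is a convenience sample, so there is no figure of its own to reproduce. The check is mainly a comparison of sections.

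**Step 1. Devices present against devices named.**

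| Device during a hold | Where the plan brings it in | Loss named as an adverse effect (section B)? | Data item for its loss named (section C, Data collected)? |
|---|---|---|---|
| Central line | C, Inclusion criteria | Yes, item 2 | No |
| Peripheral arterial line | C, Inclusion criteria (caution) | No | No |
| Peripheral venous line | C, Inclusion criteria (any access type) | No | No |
| CPAP or cannula interface | C, Inclusion criteria | No | No |
| Esophageal probe | B item 1; C, Intervention | No | No |
| Endotracheal tube | Excluded | Mentioned, but cannot occur | Not applicable |

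Four device types that enrolled infants may carry are outside the list. Even the central-line item has no operational definition and no named data field.

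**Step 2. Does another rule pick these losses up?** The saturation limit in section C, Intervention, is a rule for ending the session, and the text does not call it an adverse event. If it is counted as one, it catches a respiratory interface loss that takes saturation below 90%. It does not catch an interface loss without that fall, and losing a peripheral line or the probe need not change saturation.

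**Step 3. Scale, under assumed rates.** Let p be the chance per hold of losing a device other than a central line. The documents do not give p; the values below are assumptions. With n = 10 independent holds, the expected number is 10p and the chance of at least one is 1 − (1 − p)^10.

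- p = 0.02: expected 0.2; 1 − 0.98^10 = 0.183
- p = 0.05: expected 0.5; 1 − 0.95^10 = 0.401
- p = 0.10: expected 1.0; 1 − 0.90^10 = 0.651
- p = 0.20: expected 2.0; 1 − 0.80^10 = 0.893

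**Step 4. What a clean result would mean.** For 0/10, the exact one-sided 95% upper limit is 1 − 0.05^(1/10) = 0.259. The upper end of a two-sided 95% interval is 1 − 0.025^(1/10) = 0.308. Either limit would apply only to the event types that were counted.

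**The case against.** A reader might infer that every other device loss is bound to be scored as no event. The documents do not support that. Section B describes potential effects and does not say that its list is closed, and no sentence says that unlisted events are ignored. The backward reference in section D could also take in the temperature and saturation criteria of section C, which would bring in some respiratory losses. The holding protocol is cited as an attachment and the database fields are not listed; neither is in the supplied text, and either may contain line or device items. This part of the objection stands and limits the claim to what the supplied text names.

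A reader might also infer that a displaced probe would spoil the temperature data without anyone noticing. That is not supported either. Readings every 2 minutes give about 30/2 = 15 in a full hold with a nurse assisting, so a lost probe would probably appear as a missing or abrupt value. Similarly, blood pressure is recorded and the cuff schedule depends on whether an arterial line is in place, so losing that line could leave a trace. A trace in the data is still not a counted event.

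Nor is it right to say that the stated rate is biased downward. Leaving out an event type narrows the endpoint; it does not distort the rate of the events that are defined. Finally, counting every small shift of a cannula is a matter of convention, and the historical database may hold no comparable record. Both points stand and shape the fix. What survives is the mismatch between the devices that the plan admits, one of which it specifically warns about, and the single device class that it names as at risk.

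**Conclusion.** The concern holds in a limited form. In the supplied text, loss of a peripheral arterial or venous line, a respiratory interface or the esophageal probe is neither named as an adverse event nor given a data item. The Aim 1 safety count may therefore be incomplete for harms that come directly from moving the infant.

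The size is unknown. The 40%, 65% and 89% figures rest on assumed rates of 5%, 10% and 20% per hold and on independent holds. They also treat all ten holds as equally exposed, whereas infants without respiratory support or an arterial line are eligible, so exposure will differ between infants. The conclusion would weaken if the attached holding protocol or the database already defines and records these losses. It is worth settling before enrolment, because a bedside event that nobody was asked to record may not be recoverable afterwards.

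**What to change.** In section B, item 2, define as a recorded adverse event any unplanned displacement of an attached device (central line, peripheral arterial or venous line, CPAP or cannula interface, esophageal probe) that needs replacement or repositioning or ends the hold. The window runs from the start of transfer out of the isolette until return. State in section D which events the backward reference covers, including whether the section C session-ending criteria count.

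Add the item to section C, Data collected, and record it prospectively for each hold, including when nothing happened. Note which devices each infant has. Report by device as n/N with an exact confidence interval, where N is the number of infants with that device. Keep this descriptive, and limit the historical comparison to event types that the database records in the same way.

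The cost is a few sentences and one recording line per hold. The reported event count may rise, some event types will have no historical comparator, and intervals for devices carried by only a few infants will be very wide. Care does not change.
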